## 1 Introduction

### 1.1 Background

Psoriasis is a chronic relapsing inflammatory skin disease with an estimated prevalence of 0.32% in children under the age of 18 in 1996 (National Center for Health Statistics of the Centers for Disease Control and Prevention 1996). Since then, more epidemiologic studies have provided estimates on the prevalence of psoriasis in children in Europe and the USA.

- In the United Kingdom, prevalence of psoriasis was 0.55% in children aged 0 to 9 years and 1.37% in children and adolescents aged 10 to 19 years, with a higher prevalence in girls than in boys ([Gelfand 2005](#)).
- In Germany, 0.71% of children were affected by psoriasis and the prevalence increased from 0.12% at the age of 1 year to 1.2% at the age of 18 years ([Augustin 2010](#)).
- Results from a survey among dermatologists and general practitioners in the Netherlands suggested a prevalence of 0.37% in children aged 0 to 10 years, and 1.09% in children aged 11 to 19 years ([de Jager 2009](#)).
- In the USA, a Southern California study in children enrolled in an integrated health plan reported a 0.30% prevalence of psoriasis in children aged 2 to 19 years. The prevalence increased consistently after 5 years of age and was higher in females than in males. Stratification by gender (males vs. females) and age group yielded an overall prevalence of 0.17 % vs 0.21%; ages 2-5 years, 0.03% vs. 0.04%; ages 6-11 years, 0.16% vs. 0.15%; ages 12-19 years, 0.25% vs. 0.33% ([Wu 2011](#)).

The incidence of psoriasis in childhood in the US has been shown to increase with increasing age but also in recent years. Incidence of psoriasis in children increased significantly from 29.6 per 100,000 in 1970-1974 to 62.7 per 100,000 in 1995-1999 ([Tollefson 2010](#)).

Plaque psoriasis affects 80 to 90% of all psoriasis subjects of all age-groups ([Griffiths 2007](#); [Pariser 2007](#)) and hence is the most common variant in pediatric subjects. Most children manifest with plaque psoriasis in patterns similar to adult subjects, with lesions localized to the scalp, post auricular region, elbows, and knees; however, lesions in children are often smaller, thinner, and less scaly than those seen in adults. Involvement of the face and flexural regions is more common in children than adults, and psoriatic lesions in the diaper area are prevalent during infancy.

As in adults, pediatric psoriasis is frequently associated with significant co-morbidities like diabetes mellitus, Crohn's disease, obesity, hypertension, high cholesterol, psychological and psychiatric impact. The overall rate of comorbid conditions in psoriasis subjects under 20 years of age is double that of their peers who do not have psoriasis ([Augustin 2010](#)). A pediatric study using an international cohort of psoriasis subjects found that a significantly higher percentage of children with psoriasis showed excess adiposity (37.9% vs. 20.5%) or obesity (20.2% vs 7.3%), significantly higher than the general pediatric population ([Paller 2013](#)).

The psychological impact of psoriasis can be particularly traumatic to children and adolescents. In children with at least one of 12 different skin diseases, children with psoriasis reported the greatest impairment to quality of life. Itch or pain was reported in the same study as the most significant problem affecting their health-related quality of life ([Beattie 2006](#)). Psoriasis, a

debilitating and disfiguring skin condition, is an independent risk factor for psychiatric comorbidities in children and adolescents. Compared with a matched psoriasis-free control cohort in a study based on health services claims data in the USA, pediatric subjects had approximately 25% to 30% greater risks of being given a diagnosis of any psychiatric disorder, depression, or anxiety subsequent to the psoriasis diagnosis ([Kimball 2012](#)).

Due to the higher prevalence of plaque psoriasis in children compared to other types and the significant physical and psychological burden it carries in the pediatric population, Novartis plans to study secukinumab in the treatment of plaque psoriasis in patients from 6 to less than 18 years of age.

The treatments for psoriasis have expanded over the past decade though in children treatment is frequently off-label. The use of topical therapy in childhood is the first line of treatment for skin-limited disease. With chronicity of illness and in more severe cases, phototherapy and systemic therapy are added to help induce remission ([Silverberg 2009](#)).

Topical therapies represent the vast majority of prescriptions (57 to 91%), while systemic agents are rarely used (4%), and biologics being even more rarely used (0.4%) ([Wu 2011](#), [Kimball 2012](#)). Commonly used topical treatments for psoriasis include corticosteroids, coal tar, anthralin, calcipotriol either alone or in combination with topical steroids, tazarotene and calcineurin inhibitors ([Burden 1999](#), [Farber 1999](#), [Benoit 2007](#)). None of these treatments have been approved for the treatment of psoriasis in children below 12 years of age. Phototherapy is extensively used in adults and is a treatment option for some children with widespread plaques. Narrow-Band-UVB is considered the first-line phototherapy because it is similarly effective as Psoralen + UVA (PUVA), more convenient, and less carcinogenic ([Van Weelden 1990](#)). PUVA therapy is not generally recommended in children, but may be used with caution in adolescents ([Burden 1999](#)).

Systemic therapy is usually considered if the disease is moderate to severe in intensity, and not adequately controlled by topical therapies. Systemic treatments approved for use in adult psoriasis include acitretin, methotrexate, cyclosporine, and biologics. Acitretin is approved for subsets of psoriatic pediatric patients in some EU countries and Switzerland. However cyclosporine and methotrexate are not currently approved for the treatment of children/adolescents suffering from psoriasis. While there is no biologic approved for the treatment of psoriasis in subjects below the age of 18 years in the USA, etanercept, adalimumab and infliximab are tumor necrosis factor-alpha inhibitors that are used for the treatment of pediatric autoimmune diseases and have been used off-label to treat pediatric subjects with psoriasis ([de Jager 2010](#), [Luu 2013](#)). In Europe, Enbrel (etanercept) was approved in 2011 for *“Treatment of chronic severe plaque psoriasis in children and adolescents from the age of 6 years who are inadequately controlled by, or are intolerant to, other systemic therapies or phototherapies”*. Approval was based on a double-blind, placebo controlled study in moderate to severe pediatric subjects ([Paller 2008](#)); a retrospective analysis of results in severe subjects aged from 8 to 17 years showed that PASI 75 at Week 12 was achieved in 54.7% of subjects receiving etanercept vs. 11.3% of subjects receiving placebo,  $p < 0.001$  ([Landells 2010](#)).

Use of methotrexate, cyclosporine, retinoids (particularly acitretin), and, with a much lower frequency, dapsone and hydroxyurea has been reported in the literature ([Zappel 2004](#); [Benoit 2007](#)). Most experience has been reported with retinoids, but the potential effect on bone growth

and teratogenicity limit their use in children and adolescents. Use of cyclosporine and methotrexate is limited by their adverse event (AE) profile (kidney dysfunction, hypertension and liver dysfunction, respectively). Reports on the use of biologics in pediatric patients are scarce ([Benoit 2007](#)).

In summary, a very limited number of systemic drugs for the treatment of psoriasis are approved for children, and the few approved drugs all have severe limitations. There is a high medical need to evaluate the treatment of psoriasis in patients less than 18 years of age where controlled studies are mostly missing ([Burden 1999](#); [Farber 1999](#); [Benoit 2007](#); [Paller 2008](#)).

[figure not shown]
Secukinumab (AIN457) is a recombinant high-affinity fully human monoclonal anti-human Interleukin-17A (IL-17A) antibody of the IgG1/κ-class. Secukinumab binds to human IL-17A and neutralizes the bioactivity of this cytokine. IL-17A is the central lymphokine of a newly defined subset of inflammatory T cells, the Th17 cells which, in several animal models, are pivotal in several autoimmune and inflammatory processes. IL-17A is mainly produced by memory effector CD4+ and CD8+ T lymphocytes. IL-17A is being recognized as one of the principal pro-inflammatory cytokines in immune mediated inflammatory diseases. Its neutralization is expected to treat the underlying pathophysiology of immune mediated disease, and as a consequence provide relief of symptoms.

In adult phase II/III studies, secukinumab 300 mg and 150 mg has been shown to be efficacious with an acceptable safety profile, with secukinumab 300 mg comparable to 150 mg and both doses comparable to placebo over 12 weeks and etanercept over 52 weeks of treatment ([Langley 2014](#)).

Based on the natural history of psoriasis and the similar clinical features and histology in adults and pediatric population ([Burden 1999](#); [Farber 1999](#); [Benoit 2007](#)), it is expected that a human monoclonal antibody such as secukinumab will have an identical mode of action in children and would be metabolized similarly when compared to adults. Now that efficacy and safety have been demonstrated in adults in a comprehensive phase II/III program, it seems appropriate that the pediatric population can be exposed to secukinumab in long term studies with a dosing regimen that is extrapolated from the adult efficacious dose.

## 1.2 Purpose

The purpose of this study is to demonstrate superior efficacy of secukinumab versus placebo at Week 12, based on both PASI 75 and IGA mod 2011 0 or 1 response rates in children and adolescents aged 6 to less than 18 years with severe chronic plaque psoriasis who are candidates for systemic therapy because of: (1) inadequate control of symptoms with topical treatment, or (2) failure to respond to or tolerate previous systemic treatment and/or UV therapy. Moreover, this study will assess the long term safety and tolerability of secukinumab in this pediatric age group.

[figure not shown]
## **2 Study objectives**

### **2.1 Primary objective(s)**

To demonstrate the superiority of secukinumab (low and high dose) in pediatric subjects with severe chronic plaque psoriasis with respect to both PASI 75 and IGA mod 2011 0 or 1 response (co-primary endpoints) at Week 12, compared to placebo.

### **2.2 Secondary objectives**

- To demonstrate superiority of secukinumab (low and high dose) in subjects with severe chronic plaque psoriasis with respect to PASI 90 response at Week 12, compared to placebo.
- To assess efficacy of secukinumab in subjects with severe chronic plaques psoriasis with respect to PASI 50 and PASI 100 at Week 12, compared to placebo.
- To assess efficacy of secukinumab in subjects with severe chronic plaque psoriasis with respect to PASI 50, PASI 75, PASI 90 , PASI 100 and IGA mod 2011 0 or 1 at Week 16 and over time up to Week 52.
- To assess the efficacy of secukinumab with respect to changes in PASI score and IGA mod 2011 score at Week 12, compared to placebo, and over time up to Week 52.
- To investigate the effects of treatment with secukinumab with respect to changes in CDLQI at Week 12, compared to placebo, and over time up to Week 52.
- To investigate the effects of treatment of secukinumab with respect to CDLQI 0 or 1 achievement at Week 12, compared to placebo, and over time up to Week 52.
- To evaluate the effects of treatment of secukinumab on disability at Week 12 and over time up to Week 52 by use of the Childhood Health Assessment Questionnaire (CHAQ®), for subjects with history of psoriatic arthritis.
- To investigate the clinical safety and tolerability of secukinumab as assessed by growth, weight gain, tolerability of s.c. injections, vital signs, clinical laboratory variables, ECGs, and adverse events monitoring, compared to placebo.

### **3      Investigational plan**

#### **3.1      Study design**

[figure not shown]
This is a multicenter, randomized, double-blind, placebo- and active-controlled (etanercept in single blinded arm) study in pediatric subjects aged 6 years to less than 18 years with severe chronic plaque psoriasis. Approximately 160 subjects aged 6 years to <18 years will be enrolled, of which at least 30 will be 6 years to <12 years old. It is expected that subjects will be enrolled at approximately 70 study sites worldwide.

Two age subgroups will be studied in a staggered approach within this clinical study: 12 to less than 18 years of age, and 6 to less than 12 years of age (age for the subgroups determined at the time of randomization). Enrolment of children aged 6 to less than 12 years will begin after a favorable recommendation by an independent external Data Monitoring Committee (DMC) who will review data of approximately 80 (approximately 40 treated with secukinumab) enrolled adolescents (aged 12 to less than 18 years) treated for 28 weeks. Adolescents will continue to be recruited while the data from the first 80 subjects are being collected and analyzed.

Subjects will be randomized using a 1:1:1:1 ratio into one of the treatment arms: secukinumab low dose, secukinumab high dose, etanercept or placebo. Subjects randomized to secukinumab treatment arms (high dose and low dose) will receive dose based on the weight category (<25 kg, 25 to <50kg,  $\geq$ 50 kg). If a subject moves into a higher or lower weight group at two consecutive visits with weight measurements during the maintenance (from Week 12 onwards as assessed at monthly visits, i.e. Week 13, 14, 15 will not be taken into account) or during extension treatment period (as assessed at scheduled site visits), the subject will receive dosing according to the new (higher or lower) weight group respectively.

**Figure 3-1** Study design

The study consists of 5 Epochs: screening (up to 4 weeks), induction (of 12 weeks), maintenance (of 40 weeks), extension treatment epoch (open-label of 184 weeks) and post-treatment follow-up epoch (of 16 weeks). An outline of the visits is presented in [Figure 3-1](#), while a detailed visit and assessment schedule can be found in [Table 6-1](#), [Table 6-2](#).

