**Figure 3-2      Average concentration for the proposed low dose and high dose secukinumab arms**

Extrapolation of the exposure in children / adolescents in a bodyweight range down to 20 kg to allow maintaining exposure levels similar to those observed in adults with 50 kg body weight led to selection of 75mg, 150 mg and 300 mg within weight categories as follows:

Subjects  $\geq 50$  kg: 150 mg (low dose group) or 300 mg (high dose group)

Subjects 25 kg to  $< 50$  kg: 75 mg (low dose group) or 150 mg (high dose group)

Subjects  $< 25$  kg: 75 mg (for both dose groups in order to ensure no overly high exposures in this sub-population).

The dosing regimen used is consistent with that of adults and the total study duration including one year of blinded treatment plus the open-label extension treatment epoch and follow-up epoch ( $> 5$  drug half-lives) will allow for assessment of long term safety and efficacy.

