#### **5.2 Treatment arms**

Subjects will be randomized using a 1:1:1:1 ratio into one of the treatment arms mentioned below. Subjects randomized to secukinumab treatment arms (high dose and low dose) will receive dose according to the weight category (<25 kg, 25- <50kg,  $\geq$ 50 kg). Subjects in the two secukinumab arms weighing  $\geq$ 50kg will receive 150 mg (low dose group) and 300 mg (high dose group), 25 to <50 kg will receive 75mg (low dose group) and 150 mg (high dose group) and <25kg will receive 75mg for both dose groups. In order to maintain the treatment blind, all subjects in secukinumab or placebo arms will receive 2 s.c. injections at each dose, except for subjects <25kg weight category who will receive only 1 injection of either 75 mg secukinumab or matching placebo ([Table 5-1](#)).

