**Table 2-5 Subgroups definitions**

| Subgroup variables          | Categories                                   | Description  | Label for outputs         | Suffix for outputs* |
|-----------------------------|--|--|---------------------------|---------------------|
| Randomization weight strata | body weight stratum
(kg:<25, 25-<50, ≥50) |  | Weight strata             | A                   |
| Randomization age strata    | (<12 years or ≥12 years)                     |  | Age strata                | B                   |
| Previous systemic therapy   | Yes, No
Failure* (Yes, No)                | * at least one therapy with lack of primary efficacy or lack of secondary efficacy or lack of tolerability | Previous systemic therapy | C                   |

\*: only for “Previous < systemic > therapy” and embedded subgroup “failure”.

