**Table 2-6 Subgroup analyses**

| Endpoint/analysis                   | Randomization strata including age and weight | Previous psoriasis therapy* |
|-------------------------------------|---|-----------------------------|
| PASI 75/90 response @ Week 12       | X   | X                           |
| IGA mod 2011 0/1 response @ Week 12 | X   | X                           |
| Adverse event                       | X   |                             |

Note: presented are only those endpoints that need subgroup analyses.

\*: only for “Previous < systemic > therapy” and embedded subgroup “failure”.

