Additional dose administration listing at weeks 13, 14 and 15 will be created for IRT dosing error affected subjects. Also, subjects who changed dose due to change of weight group will be listed.

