**Exposure adjusted incidence rates will be also provided for the entire treatment period, by the following subgroups:**

- Treatment emergent AEs by SOC, PT and by age strata
- Treatment emergent AEs by SOC, PT and by body weight strata
- Treatment emergent SAEs by SOC, PT and by age strata
- Treatment emergent SAEs by SOC, PT and by body weight strata
- Important identified and potential risks (level 1) based on all adverse events by age strata
- Important identified and potential risks (level 1) based on all adverse events by body weight strata

The crude incidence of treatment emergent adverse events will be summarized by primary system organ class and preferred term. Confidence intervals for the crude rate will be derived as described in [Section 5.1](#). In addition, exposure time-adjusted rates (incidence rate) including 95% confidence intervals may be provided.

AEs and serious AEs will be summarized by presenting, for each treatment group (including any AIN457), the number and percentage of subjects having any AE, having an AE in each primary system organ class and having each individual AE (preferred term). Summaries (crude incidences only) will also be presented for AEs by severity. If a particular AE 'severity' is missing, then this variable will be listed as missing and treated as missing in summaries. If a subject reported more than one adverse event with the same preferred term, then the adverse event with the greatest severity will be presented. If a subject reported more than one adverse event within the same primary system organ class, then the subject will be counted only once with the greatest severity at the system organ class level, where applicable.

AEs and SAEs will be presented in terms of exposure time-adjusted incidence rates with 95% confidence intervals for entire study period (up to EOS).

Adverse events will also be summarized by standardized or customized MedDRA queries (SMQ or CMQ/NMQ). The MedDRA version used for reporting the adverse events will be described in a footnote.

The most common adverse events reported ( $\geq z\%$  in any group for each preferred term in the table by SOC and PT or  $\geq z\%$  in any group for each grouping term table) will be presented in descending frequency according to its incidence in secukinumab group starting from the most common event. Here, the threshold value  $z$  is set to 4 (%) but it may be updated following review of the dry run outputs.

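### Long-term secukinumab safety rates are tabulated only by weight at randomization, while the dose follows the child's current weight band, so three of the six dose-group rows come to mix mg doses

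*Protocol*

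**What the plan says.** **Dosing.** Protocol 3.1 ties the secukinumab dose to weight band. After two consecutive weight visits in a new band, in maintenance (from Week 12) or extension, "the subject will receive dosing according to the new (higher or lower) weight group respectively". Protocol 5.2 sets the two lower bands: "25 to <50 kg will receive 75mg (low dose group) and 150 mg (high dose group) and <25kg will receive 75mg for both dose groups". From 50 kg upwards the doses are 150 mg (low) and 300 mg (high). Protocol 3.3 explains the single dose below 25 kg: it was chosen "in order to ensure no overly high exposures in this sub-population".

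**Safety subgroups.** SAP Table 2-5 defines the weight subgroup as "Randomization weight strata". Table 2-6 marks adverse events under "Randomization strata including age and weight". SAP 2.9.1 then plans exposure-adjusted incidence rates (EAIRs) over the entire treatment period for AEs, SAEs and important risks by weight; one line reads "Treatment emergent SAEs by SOC, PT and by body weight strata".

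**Treatment columns.** For the entire treatment period, SAP 2.9 uses any low dose, any high dose and any secukinumab dose, with etanercept beside them. Under SAP 2.2, actual treatment departs from randomized treatment only if it was wrong for a whole period, so a planned weight-driven dose change moves nobody.

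**Dose changers.** SAP 2.5.1 says "subjects who changed dose due to change of weight group will be listed". The groups by weight and mg dose in SAP 4.1 are applied to baseline summaries and PASI/IGA response (SAP 2.4.2, 2.7.3), and no AE rate is assigned to them in the visible text.

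**The concern.** The children are growing and can be treated for about four and a half years. A child randomized at 22 kg stays in the <25 kg row throughout, even if most of that time is spent above 25 kg and, in the high-dose arm, on 150 mg instead of 75 mg. Protocol Table 9-1 prints one mg value per weight row for the entire study, which invites reading each row as the safety of one dose.

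The dosing scheme rests on exposure at low weight, and long-term safety is a stated purpose of the study. Yet no visible table gives a long-term AE rate by the dose actually received or by the band the child was in at the time. An excess of events at one band or dose could be spread over, or credited to, another row.

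**Working it through.** **1. The plan's own dose count.** Protocol 5.5.4 gives 6, 13 and 46 injections for the <25 kg group in induction, maintenance and extension. From the schedule:
- Weeks 0, 1, 2, 3, 4, 8 = 6.
- Weeks 12-15 (4) plus Weeks 16-48 every 4 weeks (9) = 13.
- Weeks 52-232 every 4 weeks = 46.

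All three are reproduced. For a child on secukinumab from randomization, Weeks 13-15 are placebo, so active doses number 6 + 1 + 9 + 46 = 62. The first pair of visits that can trigger a change is Weeks 12 and 16. Doses from Week 16 on: 9 + 46 = 55, and 55/62 = 89%. Most dosing therefore happens when a change is possible.

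**2. Which rows mix mg doses through growth.** From the doses in Protocol 5.2:

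| Row (weight at randomization) | Low dose, after one upward move | High dose, after one upward move |
|---|---|---|
| <25 kg | 75 to 75 mg: no mix | 75 to 150 mg: mix |
| 25-<50 kg | 75 to 150 mg: mix | 150 to 300 mg: mix |
| >=50 kg | 150 mg: no mix | 300 mg: no mix |

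Three of six rows mix. The low-dose <25 kg row keeps 75 mg but mixes time below and above 25 kg. Three doses in one arm's row needs a high-dose child to go from <25 kg to >=50 kg. The any-secukinumab column also holds several doses, partly because it pools the arms.

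**3. How much time falls after the change.** The documents give no growth rate and no weight distribution, so these are assumptions: linear gain, no dropout, visits at the weeks of Protocol Tables 6-1 and 6-2, and a switch at the second consecutive visit at or above the threshold. Share = mean of max(0, H - switch week)/H, for follow-up to week H.

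| Baseline and gain | H = 52 | H = 104 | H = 236 |
|---|---|---|---|
| Uniform 18-25 kg, 2 kg/year | 11% | 22% | 54% |
| 3 kg/year | 16% | 33% | 68% |
| 4 kg/year | 21% | 44% | 75% |

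For 25-<50 kg (uniform) at 3-5 kg/year, the share to Week 236 is 23-39%.

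These are shares of time in another band. In the <25 kg row, the share on another mg dose from that move is the full figure in the high-dose arm and zero in the low-dose arm. With equal arms it is about half in the pooled column (54/2 = 27% to 75/2 = about 38% at Week 236).

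**4. Effect of first-event counting.** SAP 5.1.4.1 counts time only to the first event. With constant rate r, change at time c and horizon T, the share of at-risk time after the change is (exp(-rc) - exp(-rT))/(1 - exp(-rT)). Take T = Week 244 (last dose at Week 232 plus 84 days, i.e. 12 weeks) and an assumed change at Week 104, so c = 104/52.18 = 1.99 years and T = 4.68 years. Without events the share is 140/244 = 57%.

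| Events per year (assumed) | Share after change |
|---|---|
| 0.02 | 56% |
| 0.2 | 46% |
| 1.0 | 13% |
| 2.0 | 2% |

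SAEs and important risks keep nearly the full mixing; common AEs keep little of it.

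**The case against.** Several arguments on the other side stand.

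- **Baseline strata are legitimate.** The treatments compared are weight-tiered regimens, meant to keep exposure comparable across weights. A row by weight at randomization shows the safety of starting that regimen at that weight. It misleads only if read as one mg dose or one current weight.
- **The split table has its own weakness.** Current band is post-baseline and tied to age and time on treatment, so later bands reflect later exposure. Cells are small. Assume 36 secukinumab children start below 25 kg (0.30 × 160 × 3/4) with no dropout. Pre-change time is then 36 × 236/52.18 = 163 patient-years times 0.25 to 0.46, or about 41-75. At an illustrative 8 SAEs per 100 patient-years that is 3-6 events, with 95% intervals of roughly 1.5-21 to 2.9-17 per 100.
- **Part of the ground is covered.** Dose changers are listed and AE rates are also given by age. Parts of the SAP are redacted, so the gap can be asserted only for the visible text.

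Two stronger readings are tempting and not supported. A reader might infer that every weight row mixes two or three doses; the dose table shows that growth does this in three of six. A reader might also infer that 54-75% of a true excess in small children would be lost. That only restates the assumed share of time at Week 236 with made-up event rates, since the documents give no SAE rate by weight.

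**Conclusion.** The point holds in a limited form. Beyond Week 12, dose and weight-band membership can change, while the long-term AE, SAE and important-risk rates stay fixed to the stratum at randomization. Mg doses then mix in high-dose <25 kg, low-dose 25-<50 kg and high-dose 25-<50 kg. The >=50 kg rows do not mix through growth.

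The row counts follow from the documents. The time shares rest on the growth and baseline-weight assumptions above. On those assumptions the <25 kg row is mostly post-change time by Week 236, but not by Week 52 or Week 104. The consequence is mainly for rare events. These are descriptive tables with no hypothesis test, so nothing in the primary analysis is touched; what is missing is a description of long-term safety by band and dose received.

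One passage check is needed. Protocol 5.5.5 allows no dose adjustment, and the extension paragraph of 3.1 carries forward the dose held at the end of maintenance. Both must be reconciled with the weight rule in 3.1. The listing in SAP 2.5.1 presupposes that such changes occur.

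**What to change.** Keep the planned tables in SAP 2.9.1 and label them *weight at randomization*. For periods beyond Week 12, add EAIR tables for secukinumab children, SAEs and important risks first:

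- Attribute person-time and events to the weight band and mg dose in force at onset.
- Run the first-event clock of SAP 5.1.4.1 from first dose without restarting it at a band change. A child then contributes time to each band until the first event. For each band b the rate is D_b/T_b, and the D_b and T_b add up to the D and T of the unsplit analysis, which gives a programming check.
- Report, per row of the existing tables, how many children changed band or dose and their person-years after the change.

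**Cost.** SAP wording and programming. Weight is entered in IRT, IRT tracks dosage changes, and every dose is in the dosage administration eCRF; no new data or visits are needed.

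**Downside.** Small cells with wide intervals; later bands reflect later exposure; a child can appear in more than one row; and an event just after a change may belong to the earlier dose. Footnotes should say so.
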